5.12 Safety Analyses

The safety analyses will be presented by the treatment received for the Safety Set.

5.12.1 Adverse Events

Adverse events will be coded by Primary System Organ Class (SOC) and Preferred Term (PT) using MedDRA dictionary.

5.12.1.1 *Summary of treatment emergent adverse events*

A summary of the number of treatment emergent adverse events, number and percentage of patients with at least one AE will be presented, including:

- AE

STATISTICAL ANALYSIS PLAN		
InFlectis BioScience	Sponsor:	InFlectis BioScience
	Protocol Number:	P288ALS
VERSION 1.0 NOV 12, 2024		

- TEAE
- TEAE related to study drug
- Serious TEAE
- Serious TEAE related to study drug

- Fatal TEAE
- Fatal TEAE related to study drug

- Grade 1 (mild) TEAE
- Grade 2 (moderate) TEAE
- Grade ≥ 3 (severe) TEAE

- Grade ≥ 3 TEAE related to study drug
- Grade ≥ 3 and serious TEAE
- Grade ≥ 3 and serious TEAE related to study drug

- TEAE possibly related to Riluzole

- TEAE leading to temporary discontinuation of study drug
- TEAE leading to definitive discontinuation of study drug
- TEAE leading to premature withdrawal from the study

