2. STUDY OBJECTIVES AND ENDPOINTS

Objectives	Endpoints
Primary	
To assess the safety of the test product, IFB-088 50 mg/day, in patients with bulbar-onset ALS.	
 Incidence, grade and relationship to IFB-088 for treatment emergent AEs, SAEs, and AESIs, AEs leading to dose interruption or premature discontinuation.
Secondary and exploratory	
 Change in ALSFRS-R score from baseline to month 3 and to month 6, Worsening according to ALS-MITOS score, i.e. progression to a higher stage at 3 and at 6 months compared to the baseline, Change in King's College score from baseline to month 3 and to month 6. 
Exploratory endpoints:
 
 Assessment of respiratory function (slow vital capacity [SVC], sniff test [optional], arterial blood gases [ABG]). Evaluation of nutritional status and body composition by bioelectrical impedance.
To determine the PK parameters of IFB-088.	
Measurements of PK parameters:
 
 Plasma concentration of IFB-088 and IFB-139, AUC of IFB-088 and IFB-139, Maximum observed plasma concentration (C_{max}), with associated T_{max}, Terminal or apparent terminal half-life ($t_{1/2}$), Apparent systemic clearance, apparent volume of distribution.

To investigate the effects of IFB-088 on potential biomarkers.	
 Change in TDP-43 plasmatic concentration from baseline to 6 months, compared to placebo, Change in neurofilament (NfL) light chain and NfL heavy chain plasmatic concentration from baseline to 6 months, compared to placebo, Change in plasmatic (neuro)inflammatory biomarkers from baseline to 3 months, and from baseline to 6 months, compared to placebo, Change in plasmatic oxidative stress biomarkers from baseline to 3 months and from baseline to 6 months, compared to placebo.
To investigate the QoL of ALS patients.	Change in ALS assessment questionnaire (ALSAQ-40) from baseline to 6 months.

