5.3 WITHDRAWAL OF THE PATIENT

Patients may withdraw from the study at any time without having to provide justification and without penalty to their continuing medical care.

The investigators may withdraw patients from the study for the following reasons:

- Patient withdrawing the consent,
- If, in the investigator's opinion, continuation in the study would be detrimental to the patient's well-being, in particular in case of an AE,
- If, in the investigator's opinion, the patient is unable to maintain the schedule or is non-compliant,

¹¹ Decline will be calculated as follows: 48 minus ALSFRS-R score at the time of inclusion divided by number of months since occurrence of first symptoms of disease, as reported by the patient.

- If the patient becomes pregnant during the study,
- If the patient meets one of the following criteria for permanent drug discontinuation:
 - Increased ALT or AST levels $\geq 5 \times$ ULN.
 - ALT or AST > 3 ULN and total bilirubin levels > 2 ULN.
 - Neutropenia.
 - Symptoms evocative of interstitial lung disease: dry cough and/or dyspnoea, bilateral diffuse lung opacities.
- Lost to FU. A participant will be considered lost to FU if he/she repeatedly fails to return for scheduled visits and is unable to be contacted by the study site. Site personnel are expected to make diligent attempts to contact participants who fail to return for a scheduled visit or are otherwise unable to be followed up by the site.

The date of withdrawal and the principal reason for withdrawal must be recorded in the eCRF and in the patient's records. No additional data will be collected for withdrawn patients. Every effort must be made to contact patients who did not come back for a planned visit/contact.

Every effort will be made to ensure that patients who do not complete all study visits return to the site for the premature discontinuation visit ([Section 4.1.9](#)), as soon as possible and no later than 4 weeks after the last IMP intake. Patients who withdraw due to an AE or SAE will be given appropriate care under medical supervision until the symptoms resolve or the patient's condition becomes stable.

Patients who prematurely withdrew from the study or are lost to FU will not be replaced by new patients.

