7.4 DEFINITION OF AN ADVERSE EVENT OF SPECIAL INTEREST

An AESI (serious or non-serious) is an AE of scientific and medical concern specific to the sponsor's product or program, for which ongoing monitoring and rapid communication by the investigator to the sponsor can be appropriate.

The following will be considered as AESIs:

- Renal toxicities,
- Symptomatic hypotension grade 2 (requiring non-urgent medical intervention) or above according to common terminology criteria for adverse events (CTCAE) version 5.0,
- Hypertriglyceridaemia (HTG). A cut-off value is set at triglycerides > 5.7 mmol/L (5.0 g/L) with at least 20% increase compared to baseline value.

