7.7 RECORDING OF AN ADVERSE EVENT

The investigator must record all AEs presented or reported by the patient in the AE section of the eCRF. The start date, the actions taken (corrective treatments, dose decrease, temporary or definitive discontinuation of study product, premature withdrawal from the study, none, other) and the outcome (ongoing, recovered with/without sequelae, death) must all be recorded, and the investigator must assess the event in terms of seriousness, severity and relationship to the study products.

When possible, signs and symptoms should be reported as a diagnosis i.e. the investigator should avoid reporting only the signs and symptoms. If there is no medical diagnosis and the signs and symptoms have to be reported, the investigator should record a separate AE for each sign and symptom.

The severity of the AEs will be judged by the investigator(s) and recorded as follows:

- Mild: discomfort noticed but no disruption of normal daily activity,

- Moderate: discomfort sufficient to reduce or affect daily activity,
- Severe: inability to work or perform normal daily activity.

The relationship of the AE to the study product will be judged by the investigator(s) and recorded as follows:

- Not related: a reaction for which sufficient information exists to indicate that the aetiology is unrelated to the study drug; the subject did not receive the study medication or the temporal sequence of the AE onset relative to administration of the study medication is not reasonable or the event is clearly related to other factors (subject's clinical state, therapeutic intervention or concomitant therapy),
- Unlikely: Does not follow a reasonable temporal sequence from administration of the IMP, or is most likely related to another aetiology than the trial drug such as the patient's clinical state, environmental factors or other therapies,
- Possibly: a clinical event, including laboratory test abnormality, with a reasonable time sequence to administration of the drug but which could also be explained by concurrent disease or other drugs or chemicals,
- Probably: a clinical event including laboratory test abnormality, with a reasonable time sequence to administration of the drug, unlikely to be attributed to concurrent disease or other drugs and which follows a clinically reasonable response on withdrawal (de-challenge),

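### The primary endpoint includes the grade of adverse events, but no grading scale is named for them in general, and the degree of hepatic and neutrophil toxicity is not tabulated by arm

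*SAP*

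**What the plan says.** Protocol section 2 makes this a primary endpoint: "Incidence, grade and relationship to IFB-088 for treatment emergent AEs, SAEs, and AESIs". It names no scale.

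Protocol 7.7 gives the only general scale: "The severity of the AEs will be judged by the investigator(s) and recorded as follows". The three levels are "Mild: discomfort noticed but no disruption of normal daily activity", "Moderate: discomfort sufficient to reduce or affect daily activity" and "Severe: inability to work or perform normal daily activity". There is no laboratory criterion and no level above severe.

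CTCAE enters in one place, the AESI definition in protocol 7.4, repeated in SAP 5.2.19: "Symptomatic hypotension grade 2 (requiring non-urgent medical intervention) or above according to common terminology criteria for adverse events (CTCAE) version 5.0".

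SAP 5.12.1.1 has six rows that use the word grade: Grade 1 (mild), Grade 2 (moderate), "Grade ≥ 3 (severe) TEAE", and three combinations of Grade ≥ 3 with relatedness and seriousness. SAP 5.12.1.2 adds a listing of Grade ≥ 3 events. Grade is not defined, and the listings carry an intensity field with no separate CTCAE grade.

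Protocol 5.3 lists "criteria for permanent drug discontinuation". Three of these are laboratory-defined and require no symptoms: ALT or AST at 5 x ULN or more, ALT or AST above 3 x ULN with total bilirubin above 2 x ULN, and neutropenia. Under protocol 4.2.1.1 a laboratory abnormality is reported as an AE when the investigator finds it clinically significant.

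**The concern.** A row labelled Grade ≥ 3 suggests a numbered scale with levels above 3. The only such scale named for adverse events in either document is CTCAE, and the protocol applies it to one AESI. The levels actually recorded describe discomfort and lost activity. A reader of the report could therefore take the Grade ≥ 3 count as a statement about high-grade toxicity, including laboratory toxicity, when the recorded scale gives no rule for placing a symptomless laboratory event.

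Safety is the primary objective, and several toxicities the protocol acts on are laboratory findings. Protocol 8.1.5.1 asks for AEs to be summarised by severity, but the SOC and preferred-term table in SAP 5.12.1.2 has no severity split. The rows in 5.12.1.1 are therefore the only severity tabulation. If they need not pick up a hepatic or neutrophil toxicity, the question is whether another table shows how marked it was in each arm.

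**Working it through.** **The plan's own figure.** The only number tied to the primary safety endpoint is the chance of at least one SAE among 28 IFB-088 patients (protocol 8.1.2, SAP 3). 1 − 0.95^28 = 76.2% and 1 − 0.90^28 = 94.8%; both reproduce. They concern SAEs and are not in dispute. What follows compares passages.

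**Step 1: where a symptomless event falls.** Take ALT at 5 x ULN, judged clinically significant, with no symptoms.
- Severe needs inability to work or carry out daily activity: not met.
- Moderate needs discomfort that reduces or affects activity: not met.
- Mild needs discomfort that is noticed: not literally met either, though it is the nearest level.

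The investigator has no clear rule, and the event need not reach the Grade ≥ 3 rows.

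**Step 2: whether another table shows its degree.** Discontinuation criteria (protocol 5.3) against the classes planned in SAP 5.2.22 and Table 4:

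| Analyte | Protocol 5.3 criterion | SAP classes |
|---|---|---|
| ALT, AST | ≥ 5 x ULN; or > 3 x ULN with bilirubin > 2 x ULN | one cut, at ULN |
| Total bilirubin | > 2 x ULN, with the ALT or AST rise | cuts at LLN and ULN |
| Neutrophils | neutropenia, no count given | cuts at 1.5 and 7 x 10⁹/L |
| GFR | none listed | six classes, < 15 to ≥ 90 |
| Triglycerides | none listed | five classes, up to > 11.4 mmol/L |

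For ALT and AST, a value just above ULN and one at the 5 x ULN stopping threshold share a cell. Any neutrophil count below 1.5 falls in a single class. GFR and triglycerides are already graded, and SAP 5.12.1.2 adds a listing for triglycerides above 5.7 mmol/L with a rise of at least 20%.

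**Step 3: which visits are tabulated.** SAP 5.12.3.3 plans shift tables from baseline to V3 and V4 only. Quantitative values go to listings. SAP 5.12.3.2 defines the classes at other visits too, but with the same cuts, so tabulating them would not show degree. SAP 5.4 keeps early-termination assessments out of by-visit summaries. SAP 5.2.5 counts a premature discontinuation visit as V3 on days 83 to 99 and as V4 on days 170 to 194:
- mapped days: (99 − 83 + 1) + (194 − 170 + 1) = 17 + 25 = 42;
- unmapped days among the first 194: 194 − 42 = 152.

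This counts calendar days and says nothing about how many patients stop on them. It does show that values from a patient stopped in month 2, for example, would be listed only.

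**The case against.** The strongest reply is that such a patient is visible elsewhere. AEs leading to interruption or discontinuation are themselves a primary endpoint, with rows in the same SAP 5.12.1.1 summary. Clinically significant laboratory abnormalities over the whole study are summarised and listed. AESIs have a listing. An event judged medically important can also be an SAE. All of this stands, and it limits the harm. These outputs show that an event occurred, and the listings give its value, but none tabulates hepatic or neutrophil degree by arm.

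A second reply is that the SAP attaches mild, moderate and severe to its grade rows, so the intended meaning can be guessed. That is fair, but the link to protocol 7.7 rests on matching labels, and ≥ 3 has no meaning on a three-level scale.

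Some stronger readings are tempting and are not supported:
- **That the Grade ≥ 3 rows cannot register laboratory toxicity, or that such events must be Grade 1.** Severity is the investigator's judgement and the mild wording does not strictly fit. The documents leave a gap and do not force a result.
- **That the endpoint is formally graded on two scales.** CTCAE is only an entry threshold for one AESI.
- **That hypotension will be tabulated by grade on the wrong scale.** No hypotension-by-grade row is planned.
- **That a count of zero in the Grade ≥ 3 row would hide a known rate.** Any such figure assumes both how many patients are stopped and that all are scored mild. Protocol 5.3 sets no count for neutropenia, so a stopped patient need not be at any particular CTCAE grade.

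**Conclusion.** The point holds in a limited form. Grade is in the primary endpoint but undefined for adverse events in general, and the label ≥ 3 does not fit the scale recorded. A symptomless laboratory toxicity that meets a discontinuation criterion has no clear severity level and need not appear in the Grade ≥ 3 rows. The outputs that would catch it do not show its degree by arm.

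In extent, this touches six rows of SAP 5.12.1.1, one listing in 5.12.1.2, and the tabulation of ALT, AST, bilirubin and neutrophils. GFR and triglycerides are largely covered. No expected rate is given, so the number of patients affected cannot be stated.

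The verdict assumes that the eCRF severity field holds the three levels of protocol 7.7, as the SAP's intensity field suggests. If it also holds a CTCAE grade, one defining sentence would settle the labelling, but not the laboratory tabulation. This is an inexpensive improvement to the primary safety report that should be made; it does not invalidate the safety analysis.

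**What to change.** 1. In SAP 5.12.1.1 and 5.12.1.2, label the investigator-rated rows and listing as mild / moderate / severe (protocol 7.7), and drop the words Grade and ≥ 3.
2. In SAP 5.12.3.3, add a by-arm table of the worst post-baseline value, including unscheduled and early-termination visits, by CTCAE v5.0 laboratory grade for ALT, AST, bilirubin and neutrophils. Creatinine is optional. Neither document contains the CTCAE laboratory cut-offs, so attach them to the SAP.

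The values are already collected and no clinical rule changes. The cost is a few derived tables and table shells, and a report with two severity scales, each labelled. SAP section 5 requires approval of the SAP and shells before the blind is broken, so the change belongs before then; after final database lock it would need an addendum.

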5.12.1.2 Treatment emergent adverse events

The number of patients with at least one TEAEs and the corresponding number of events will be described by System Organ Class and Preferred Term overall in the safety population. In case a same patient presented the same AE (i.e. same event as defined according to SOC and PT) several times during the study, only one occurrence will be reported, but the total number of events will be counted. This table will be sorted by decreasing percentage of SOC and PT within SOC for the overall column.

The following listings will be edited in order to complete the AE analyses:

- All TEAE reported along the study
- TEAE related to study drug,
- Serious TEAE,
- Grade ≥ 3 (severe) TEAE,

STATISTICAL ANALYSIS PLAN		
InFlectis BioScience	Sponsor:	InFlectis BioScience
	Protocol Number:	P288ALS
VERSION 1.0 NOV 12, 2024		

- TAESIs

For each listing of AE, the following items will be included: Patient identifier, Country, Age (years), Sex, Start date of treatment - Reported term, MedDRA primary SOC, MedDRA preferred term, Start/end datetime of AE, Seriousness, Seriousness criteria, Relationship to study drug, Intensity, Outcome, Action taken regarding investigational drug, Corrective treatment, and if it is an AE of special interest.

In addition, for specific event of interest, a listing of patients with triglycerides > 5.7 mmol/L with at least 20% increase compared to baseline value will be provided. Triglycerides and Glomerular Filtration Rate will be described by classes defined in section 5.2.

5.12.2 Deaths

A listing of fatal adverse events will be provided including the same items as for AE listing described above, with in addition the primary reason for death (if available) and the date of death.

5.12.3 Laboratory Data

5.12.3.1 Parameters

5.12.3.1.1 Haematology

Haematology parameters are:

- Erythrocytes
- Hemoglobin
- Hematocrit
- White blood cells, total
- Neutrophils
- Lymphocytes
- Monocytes
- Eosinophils
- Basophils
- Platelets

5.12.3.1.2 Biochemistry

Biochemistry parameters are:

STATISTICAL ANALYSIS PLAN		
InFlectis BioScience	Sponsor:	InFlectis BioScience
	Protocol Number:	P288ALS
VERSION 1.0 NOV 12, 2024		

- Glucose
- Total cholesterol
- HDL cholesterol
- LDL cholesterol
- Triglycerides
- C Reactive Protein
- Troponin T
- Creatine Kinase
- Uric Acid

Only at V3bis visit:

- Prothrombin time
- D-Dimers
- INR
- B type natriuretic peptide (BNP)

5.12.3.1.3 Renal function (blood)

Renal function parameters are:

- Creatinine
- Blood Urea Nitrogen
- Glomerular Filtration Rate, Estimated
- Protein

5.12.3.1.4 Liver function

Liver function parameters are:

- Albumin
- Bilirubin
- Direct Bilirubin
- Alkaline Phosphatase
- Aspartate Aminotransferase
- Alanine Aminotransferase
- Gamma Glutamyl Transferase
- Lactate Dehydrogenase

STATISTICAL ANALYSIS PLAN		
InFlectis BioScience	Sponsor:	InFlectis BioScience
	Protocol Number:	P288ALS
VERSION 1.0 NOV 12, 2024		

5.12.3.1.5 Electrolytes

Electrolytes parameters are:

- Sodium
- Potassium
- Chloride
- Bicarbonate
- Calcium
- Magnesium
- Phosphate

5.12.3.1.6 Urinalysis

Urinalysis parameters are:

Urine dipstick:

- Blood
- Leukocytes
- Glucose
- Protein
- pH

Quantitative urinary measurements:

- Beta-2 Microglobuline
- Albumin
- Creatinine
- Albumin-to-creatinine ratio
- Protein (mg/dL)

Cytobacteriological examination of urine (CBEU):

- Parameter collected during CBEU.

5.12.3.1.7 24H protein test

For patient with protein ≥ 30 mg/dL:

24h protein parameters are:

- Urine volume (mL)
- Amount of protein (mg/day)

STATISTICAL ANALYSIS PLAN		
InFlectis BioScience	Sponsor:	InFlectis BioScience
	Protocol Number:	P288ALS
VERSION 1.0 NOV 12, 2024		

- Albumine (mg/day)
- Creatinine (mg/day)
- Protein/Creatinine (RATIO)
- Investigator's overall assessment

5.12.3.1.8 Crystalluria

Only a listing of crystalluria will be done.

5.12.3.2 Expressions

For investigator's overall assessment of 24h protein test and urinalysis parameters, values will be expressed in class (Normal, Abnormal clinically significant (CS), Abnormal non clinically significant (NCS)) at baseline and at each post-baseline visit (baseline (V0), V1, V2, V3, V3bis, V4 and V-FU visit).

For hematology, biochemistry, renal function, liver function and electrolytes parameters, values will be expressed as following:

- in class according to reference ranges at each visit (Low, In range or High) at baseline and at each post-baseline visit (baseline (V0), V1, V2, V3, V4 and V-FU visit)
- quantitatively with value at baseline, at each post baseline visit, change from baseline to each post baseline visit and relative change from baseline to each post baseline visit for listing value

Note:

- for creatinine and Glomerular Filtration Rate, other visits are performed: V2 + 1 month, V3 + 1 month, V3 + 2 months
- And for urine dipstick: V0 + 1 week

5.12.3.3 Analysis

Clinically significant abnormalities in laboratory values across the whole study will be summarized and listed.

For urinalysis parameters:

Shift tables in relation with normal, abnormal CS and abnormal NCS value from baseline to V3 and V4 will be presented for each parameter.

Urinalysis data will also be listed separately for each parameter.

For 24h protein test parameters:

Shift tables in relation with normal, abnormal CS and abnormal NCS value from baseline to V3 and V4 will be presented for the investigator's overall assessment.

STATISTICAL ANALYSIS PLAN			
InFlectis BioScience	Sponsor:	InFlectis BioScience	
	Protocol Number:	P288ALS	
VERSION 1.0 NOV 12, 2024			

A listing will also be presented for patients with at least one abnormal clinically significant of 24h protein test during the study.

For hematology, biochemistry, renal function, liver function and electrolytes parameters:

Each measurement (continuous data) will be categorized as below, within, or above normal range, based on ranges supplied by the laboratory used. Shift tables in relation to the normal range from Baseline to V3 and V4 will be presented for each parameter.

Laboratory data will also be listed separately for each parameter (indicating abnormal values at each applicable follow-up time point). Quantitative value at each visit with the change from baseline and relative change from baseline will be also presented in the listing.

Table 4: Specific rules for ULN and LLN by parameters

Parameter	Units	Below normal range	In normal range	Above normal range
Glomerular Filtration Rate	ml/min/1,73 m ²	<90	≥90	NA
Basophils	10 ³ /mm ³ ou 10 ³ /uL ou 10 ⁹ /L ou G/L	NA	<0.1	≥0.1
	%	Not analysable (will be converted by data management)		
Eosinophils	10 ³ /mm ³ ou 10 ³ /uL ou 10 ⁹ /L ou G/L	NA	<0.4	≥0.4
	%	Not analysable (will be converted by data management)		
Erythrocytes	10 ¹² /L, 10 ⁶ /mm ³ , 10 ⁶ /uL, T/L	<3.8	[3.8 ;5.5]	>5.5
Hemoglobin	g/dL	<12	[12 ;16]	>16
	g/L	<120	[120 ;160]	>160
Lymphocytes	10 ³ /mm ³ ou 10 ³ /uL ou 10 ⁹ /L ou G/L	<1,5	[1,500 ; 4]	>4
	%	Not analysable (will be converted by data management)		
Monocytes	10 ³ /mm ³ ou 10 ³ /uL ou 10 ⁹ /L ou G/L	<0.5	[0.5 ; 0.8]	>0.8
	%	Not analysable (will be converted by data management)		
Neutrophils	10 ³ /mm ³ ou 10 ³ /uL ou 10 ⁹ /L ou G/L	<1.5	[1.5 ; 7]	>7
	cells/mm ³	<1500	1500 et 7000	>7000

STATISTICAL ANALYSIS PLAN				
InFlectis BioScience	Sponsor:		InFlectis BioScience	
	Protocol Number:		P288ALS	
VERSION 1.0 NOV 12, 2024				

	%	Not analysable (will be converted by data management)		
White blood cells, total	1000/uL, 10 ³ /mm ³ , 10 ³ /uL, 10 ⁹ /L et G/L	<4.5	[4.5 ; 11]	>11
Glucose	mg/dl	<70	[70 ; 110]	>110
	mmol/L	<4	[4 ; 6.1]	>6.1
	umol/L	<400	[400 ; 610]	>610
HDL cholesterol	g/L	<0.4	≥ 0,4	NA
	mg/dl	<40	≥ 40	NA
	mmol/L	<1.04	≥ 1.04	NA
LDL cholesterol	mg/dL	NA	<160	≥160
	mmol/L	NA	<4.1	≥4.1
Total Cholesterol	mg/dL	NA	<200	≥200
	mmmol/L	NA	<5	≥5
Triglycerides	g/L	NA	≤1.5	>1.5
	mg/dL	NA	≤150	>150
	mmol/L	NA	<1.71	>1.71
	umol/L	NA	<=171	>171
Alanine Aminotransferase	All units	NA	<ULN	>ULN
Aspartate Aminotransferase	All units	NA	≤ULN	>ULN
D-Dimers	All units	NA	≤ULN	>ULN
Direct Bilirubin	All units	NA	≤ULN	>ULN
Gamma Glutamyl Transferase	All units	NA	≤ULN	>ULN
Other parameters	All units	<LLN	[LLN ; ULN]	>ULN

If LLN is missing then all values below the ULN will be considered as in reference range.

If ULN is missing then all values above the LLN will be considered as in reference range.

If a value is <xx then:

- If the LLN = 0 or missing or NA then consider the value as in reference range
- Else consider the value as low reference range

If a value is >xx then:

- If the ULN is missing or NA then consider the value as in reference range
- Else consider the value as upper reference range

For Glomerular Filtration Rate:

If a value is >xx with xx<90 then consider value as below reference range

If a value is >xx with xx≥90 then consider value as in reference range

If a value is <xx then consider value as below reference range

STATISTICAL ANALYSIS PLAN		
InFlectis BioScience	Sponsor:	InFlectis BioScience
	Protocol Number:	P288ALS
VERSION 1.0 NOV 12, 2024		

Note: for all listing value of premature discontinuation and V3bis visit will be also presented when applicable.

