This will include temperature, systolic and diastolic arterial pressure and heart rate. Information about the vital signs must be present in the source documentation at the study site. Blood pressure and heart rate will be measured after the patient has rested for 5 minutes, in both supine position and standing.

4.2.1.6 *Electrocardiogram*

A standard 12-lead ECG will be performed in triplicates in a resting position. Prior to the recording the patient should be at rest for at least 5 minutes. The ECG printout will be reviewed by the investigator.

4.2.1.7 *Laboratory assessments*

Accredited local and central laboratories will be used for analysis of specimens collected at each visit, according to [Table 3](#). Analyses will include:

- Complete laboratory evaluations (hematology, biochemistry, electrolytes, liver function, renal function, urinalysis) for safety assessment,
- Biomarker assessment ([Section 4.2.2.3](#)),
- Pregnancy test,
- Crystalluria ([Section 4.2.1.9](#)),
- PK.

Laboratory values that exceed the thresholds of normal laboratory values must be commented by the investigator on source documents and respective patient's laboratory eCRF page.

For each visit, the drawn amount of blood, urine and CSF required is detailed in [Table 3](#).

Table 3 – Schedule and location of the blood, urinary and cerebrospinal fluid tests

Sample	Assessment	Screening	Baseline (V0)	V1	V2	V3	V3bis	V4	V-FU	Premature discontinuation	Bio bank	Quantity per visit	Laboratory
Whole blood (EDTA/lithium heparin tube)	Safety (haematology)	X	X*	X	X	X		X	X	X			Local
Serum (serum-separating tube)	Safety (electrolytes, biochemistry, liver function, renal function)	X	X* ^a	X	X ^{a a}	X ^{a a} ^a	X	X	X	X		20 ml	
Plasma (EDTA tube)	Biomarkers		X			X		X		X	X	20 ml	Central
Whole blood (PAXgene blood RNA tube)	Biomarkers		X					X		X	X	5 ml	Central
Plasma (lithium heparin tube)	PK				X							10 ml	Central
Plasma (lithium heparin tube)	Efficacy (arterial blood gases)	X				X		X		X		2 ml	Local
Urine	Safety	X	X* [†]	X	X	X		X	X	X		50 ml	Local
Urine	Crystalluria				X				X	X		50 ml	Central
Urine	Biomarkers		X					X		X	X	100 ml	Central
Blood/urine	Pregnancy test	X**	X***		X***	X***		X***	X**	X***		2 ml/1 ml	Local
CSF	Biomarkers	X						X		X	X	1.8 ml	Central

CSF: cerebrospinal fluid, EDTA: ethylenediaminetetraacetic acid, V: visit, FU: follow-up.

* If needed, based on investigator's judgement.

† Additional urine analysis (dipstick) at V0 + one week.

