5.1 INCLUSION CRITERIA

Patients must satisfy all the following inclusion criteria to be enrolled in the study:

1. Diagnosis of probable or definite ALS according to the revised El Escorial criteria [29], with bulbar onset of disease, familial or sporadic form,
2. Onset of symptoms \leq 18 months prior to screening, as reported by the patient,
3. Adult males or females, aged at least 18 years old,
4. SVC $>$ 60% of predicted value for age and sex,
5. ALSFRS-R score \geq 36,
6. Treatment with riluzole 100 mg/day, at stable dose since at least one month and well tolerated,
7. Male or female patient of childbearing potential¹⁰ who agrees to use highly effective mechanical contraception methods (sexual abstinence, intrauterine device, bilateral tubal occlusion, vasectomised partner) throughout the study, and for 3 months after the end of the treatment,
8. Patient who read, understood and signed the ICF,
9. Patient who is willing to adhere to the study visit schedule and is capable to understand and comply with protocol requirements.

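### SAP Table 4 sets fixed limits beside a laboratory-range rule: some classes depend on the reporting unit, and haemoglobin and erythrocytes have one range for both sexes

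*SAP*

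**What the plan says.** For haematology, biochemistry, renal, liver and electrolyte results, SAP 5.12.3.3 states: "Each measurement (continuous data) will be categorized as below, within, or above normal range, based on ranges supplied by the laboratory used". Shift tables from baseline to V3 and V4 are built on these classes.

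The same section contains "Table 4: Specific rules for ULN and LLN by parameters". It gives fixed limits for 14 parameters: GFR, basophils, eosinophils, erythrocytes, haemoglobin, lymphocytes, monocytes, neutrophils, total white cells, glucose, HDL, LDL, total cholesterol and triglycerides. ALT, AST, D-dimers, direct bilirubin and GGT are judged against the ULN. A closing row, "Other parameters", goes back to LLN and ULN for everything else. No sentence says whether a fixed limit or the laboratory's own limit prevails when both exist.

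Haemoglobin is in range from 12 to 16 g/dL and erythrocytes from 3.8 to 5.5, with no split by sex. Protocol 5.1 enrols both: "Adult males or females, aged at least 18 years old". Several chemistry rows list separate limits by unit. Conversion by data management is mentioned only for white-cell differentials reported in percent.

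Other laboratory reporting is planned as well: "Clinically significant abnormalities in laboratory values across the whole study will be summarized and listed", and "Quantitative value at each visit with the change from baseline and relative change from baseline will be also presented in the listing".

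**The concern.** Safety is the primary objective. SAP 5.12.3.2 expresses quantitative laboratory values for listings, so no by-arm summary of, say, mean haemoglobin change is specified. The shift tables are therefore the main by-arm display of haematology, though not the only one.

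If their classes depend on the unit a local laboratory happens to use, the same blood value can be normal at one site and abnormal at another. Protocol Table 3 sends safety samples to local laboratories, recruitment is in France and Italy, and Table 4 itself lists several units, so mixed reporting is foreseeable. If one haemoglobin range serves both sexes, the male rows of a shift table may be less sensitive to a fall and may show more high baselines than the laboratory's own limits would.

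**Working it through.** **1. Unit consistency, from Table 4's own figures.** Each row that gives both units implies a conversion factor.

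- HDL: 40 / 1.04 = 38.46 mg/dL per mmol/L.
- LDL: 160 / 4.1 = 39.02.
- Total cholesterol: 200 / 5 = 40.0.

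These are three factors for one substance. By the HDL row, 200 mg/dL is 200 × 1.04 / 40 = 5.20 mmol/L; by the LDL row, 200 × 4.1 / 160 = 5.125 mmol/L. In the other direction, 5 mmol/L is 5 × 38.46 = 192 or 5 × 39.02 = 195 mg/dL. A total cholesterol between 5.0 and about 5.12–5.20 mmol/L is thus above range in mmol/L and in range in mg/dL.

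- Glucose, upper pair: 110 / 6.1 = 18.03. Lower pair: 70 / 4 = 17.5.

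By the upper pair, 70 mg/dL is 70 × 6.1 / 110 = 3.88 mmol/L. A glucose from 3.88 to just under 4.0 mmol/L is below range in mmol/L and in range in mg/dL.

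Some rows do agree: haemoglobin in g/dL and g/L, neutrophils in both units, and triglycerides in mg/dL and mmol/L (150 / 1.71 = 87.7, with the same factor for all four cut-offs in SAP 5.2.22).

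**2. The µmol/L rows.** One mmol/L is 1000 µmol/L.

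| Analyte | mmol/L limit | Same limit in µmol/L | Table 4 µmol/L |
|---|---|---|---|
| Glucose | 4 to 6.1 | 4000 to 6100 | 400 to 610 |
| Triglycerides | 1.71 | 1710 | 171 |

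As labelled, a glucose of 5 mmol/L (5000 µmol/L) and a triglyceride of 1.0 mmol/L (1000 µmol/L) are both above range. The printed limits correspond to 0.61 × 110 / 6.1 = 11 mg/dL glucose and 0.171 × 150 / 1.71 = 15 mg/dL triglycerides. The figures do fit µmol/dL (factor 100), so the unit label may be the slip.

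SAP 5.2.22 repeats the triglyceride pattern. There, 1000 µmol/L (1.0 mmol/L) falls in the class 570–1140 µmol/L, which is paired with 5.7–11.4 mmol/L. SAP 5.12.1.2 reports triglycerides by these classes.

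**3. One range for both sexes.** Take a man whose laboratory has limits L to U, with L above 12 and U above 16 g/dL. Table 4 classes his values from 12 up to L as in range and those from 16 to U as above. A fall from 15.0 to 12.2 g/dL appears as in range to in range. Values under 12 g/dL are still classed low.

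The size needs L and U, which the documents do not give. *Assumption, for illustration only:* healthy male values are normal, with L to U as the central 95%, so mean (L + U)/2 and SD (U − L)/3.92. By construction 2.5% lie above U in any case, so the extra share flagged high is P(>16) − 2.5%.

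| Assumed male range (g/dL) | Width of band from 12 to L | P(>16) | Extra flagged high |
|---|---|---|---|
| 12–16 | 0 | 2.5% | 0 |
| 12.5–16.5 | 0.5 | 7.1% | 4.6% |
| 13–17 | 1.0 | 16.4% | 13.9% |
| 13–17.5 | 1.0 | 25.7% | 23.2% |
| 13.5–17.5 | 1.5 | 31.2% | 28.7% |

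The answer runs from nothing to over a quarter of healthy men, depending wholly on an input the plan does not supply.

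**The case against.** Several points on the other side have force.

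- **A default with exceptions is not a contradiction.** The table's title and its catch-all last row suggest laboratory ranges by default and fixed limits where listed. That is the likelier reading, but it is an inference. A reader might go further and say that Table 4 overrides laboratory ranges outright; the SAP does not say so.
- **Fixed limits across many local laboratories are a defensible harmonisation**, and both arms are treated alike. This stands for the principle of fixed limits. It does not cover limits that differ by unit, which defeat harmonisation.
- **The cholesterol and lower glucose mismatches are of rounding size.** True. The µmol/L discrepancy is not, but it affects results only if a site reports in that unit and nobody converts. The triglyceride event-of-special-interest threshold is stated separately in mmol/L, with its own listing.
- **Other displays remain.** Clinically significant abnormalities are summarised and listed, and safety analyses are by treatment received. Protocol 4.2.1.1 requires significant findings to be reported as adverse events. Investigators also review out-of-range results: "Laboratory values that exceed the thresholds of normal laboratory values must be commented by the investigator". All values are listed with their changes. Haematocrit has no Table 4 row, so it stays on laboratory limits and has its own shift table.

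The last point rules out two inferences a reader might draw. The shift tables are not the only by-arm view of haematology. Nor do the documents show that anaemia in men would be missed: that needs a male laboratory lower limit above 12 g/dL, and even then only the band between 12 and that limit is reclassed, while values, adverse events and significant abnormalities are still reported.

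**Conclusion.** The point holds, with limited reach. From the SAP alone, precedence between the laboratory-range rule and Table 4 is unstated. Total cholesterol and glucose limits do not match across units by the table's own factors, and the µmol/L limits are a factor of ten off the mmol/L limits if the unit label is right. Haemoglobin and erythrocytes have one range for men and women.

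The practical size is small for the cholesterol and glucose pairs (gaps of about 0.12–0.20 and 0.12 mmol/L). It would be gross for any unconverted µmol/L result, if there are any. For male haemoglobin it cannot be fixed from the documents: any single percentage of men misclassed rests on an assumed laboratory range, and the figure is zero at 12–16 g/dL.

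What is affected is the low / in range / high class, the shift tables and the abnormal flags in listings. This is worth correcting before unblinding because safety is the primary objective and the correction is cheap. It does not undermine the safety assessment as a whole.

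**What to change.** Amend SAP 5.12.3.3, Table 4 and 5.2.22 before unblinding; SAP section 5 provides for amendments up to that point.

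1. Convert every result to one unit per analyte before classing, and apply one limit per analyte. For total cholesterol and glucose, choose one member of each pair and derive the other from it.
2. Correct the µmol/L values, or the unit label, for glucose and triglycerides in Table 4 and for triglycerides in 5.2.22.
3. For haemoglobin and erythrocytes, use the laboratory's sex-specific LLN and ULN where supplied; otherwise use sex-specific fixed limits.
4. Add a sentence on precedence: Table 4 applies only where the laboratory gives no limits.

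The cost is SAP wording and minor programming. The drawback is that limits will vary slightly between laboratories, as they already do for ALT, AST and the parameters in the catch-all row.
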